#### 8.4.2 Electrocardiogram (ECG)

ECGs will be measured according to the assessment schedule in [Table 8-1](#). ECGs must be recorded after 10 minutes rest in the supine position to ensure a stable baseline. The preferred sequence of cardiovascular data collection during study visits is ECG collection first, followed by vital signs. The Fridericia QT correction formula (QTcF) should be used for clinical decisions.

Single 12-lead ECGs will be collected using the sites own ECG machines and key parameters and the original trace available within the source data.

For any ECGs with subject safety concerns, two additional ECGs must be performed to confirm the safety finding. A monitoring or review process should be in place for clinically significant ECG findings throughout the study and especially at baseline before administration of study treatment. Clinically significant abnormalities must be recorded on the CRF as either medical history/current medical conditions or adverse events as appropriate.

Any identifier details must be redacted e.g subject initials, date of birth.

### **8.4.3 Pregnancy**

All pre-menopausal women who are not surgically sterile will have serum/urine pregnancy testing. Additional pregnancy testing might be performed if requested by local requirements.

### **8.4.4 Appropriateness of safety measurements**

The safety assessments selected are standard for this indication/patient population.

## **8.5 Additional assessments**

### **8.5.1 Clinical Outcome Assessments (COAs)**

[figure not shown]
COAs are utilised on this study for assessment of study eligibility and also as part of the secondary study objectives. Those COAs related to the study objectives and efficacy are documented in protocol [Section 8.3.2](#).

The remaining COAs used on this study are documented as follows.

#### **8.5.1.1 Asthma Control Questionnaire (ACQ-5)**

In this study the ACQ-5 will be used as Exclusion criterion at screening in order to identify those subjects who are currently symptomatic and who may exacerbate during the Run-in or treatment periods.

The ACQ-5 will be self-administered at the clinic during the screening visit and it only takes a few minutes to complete. Patients will be asked to recall how their asthma has been during the previous week and to respond to the symptom questions on a 7-point scale (0=no impairment, 6=maximum impairment). The questions are equally weighted and the ACQ-5 score is the mean of the 5 questions and therefore between 0 (totally controlled) and 6 (severely uncontrolled) ([Juniper et al 1999](#); [Juniper et al 2005](#)) ([Section 16.6](#)).

## 9 Study discontinuation and completion

### 9.1 Discontinuation

#### 9.1.1 Discontinuation of study treatment

Discontinuation of study treatment for a patient occurs when study drug is stopped earlier than the protocol planned duration, and can be initiated by either the patient or the Investigator.

The Investigator must discontinue study treatment for a given patient if, on balance, he/she believes that continuation would negatively impact the risk/benefit of trial participation.

Study treatment must be discontinued under the following circumstances:

- Withdrawal of informed consent (and the Investigator must prematurely withdraw the patient from the study);
- Pregnancy;
- Female subjects non-compliant with the chosen effective method of contraception during the study: The Investigator must provide appropriate advice on the continued use of effective contraception for at least one week (at least 5 half-lives of QAW039) after study drug discontinuation and follow up with the subject as appropriate at least to the end of this period;
- Any protocol deviation that results in a significant risk to the patient's safety;
- Liver laboratory test abnormality / event (see [Section 16.2](#)):
  - Abnormal liver laboratory results requiring discontinuation – refer to [Table 16-1 - Section 16.2](#) ;
- If the Investigator considers it appropriate after the confirmation of a liver safety monitoring signal:

- ALT or AST  $\geq$  5xULN, **or**
- ALT or AST  $\geq$  2.5xULN **and** total bilirubin (TBL)  $\geq$  1.5xULN ( [Section 16.2](#) );
- Any laboratory abnormalities that in the judgment of the Investigator, taking into consideration the subject's overall status, prevents the subject from continuing participation in the study;
- Premature unblinding of study treatment for a patient for any reason; please refer to [Section 6.6.2](#) ;
- Total white blood cell count  $<$  1000 cells/ $\mu$ L;
- Patient requires SCS/OCS use for a period of more than 5 consecutive days during the study. Any OCS/SCS use in addition to this allowed 5 days of treatment will result in withdrawal;
- If patients on statin therapy complain of persistent muscle pain without any obvious cause for greater than 3 days, accompanied by an increase in CK levels  $>$ 10xULN or persistent intolerable muscle pain, regardless of the accompanying CK level;
- If a patient undergoes nasal surgery, including but not limited to the following: treatment of nasal polyposis, septal deviation correction, turbinectomy, para-nasal sinus drainage, nasal plastic surgery, hypophysis tumor nasal approach.
- If a patient develops a medical condition, that requires consistent use of prohibited treatment as per [Section 6.2.2](#) or if patient exhibits a behavior of non-compliance regarding prohibited medication.

If discontinuation of study treatment occurs, the Investigator should make a reasonable effort to understand the primary reason for the subject's premature discontinuation of study treatment and record this information.

[figure not shown]
Subjects who discontinue study treatment or who decide they do not wish to participate in the study further should NOT be considered withdrawn from the study UNLESS they withdraw their consent (see withdraw of informed consent section.). **Where possible, they should return for the assessments indicated** in the Assessment schedule ( [Table 8-1](#) ).

After study treatment discontinuation, at a minimum, in abbreviated visits, the following data should to be collected at clinic visits or via telephone visits:

- new/concomitant treatments including OCS use
- adverse events/Serious Adverse Events

If they fail to return for these assessments for unknown reasons, every effort (e.g. telephone, e-mail or letter) should be made to contact the subject/pre-designated contact as specified in the lost to follow-up section. This contact should preferably be done according to the study visit schedule.

If the patient cannot or is unwilling to attend any visit(s), the site staff should maintain regular telephone contact with the patient, or with a person pre-designated by the patient. This telephone contact should preferably be done according to the study visit schedule. The information already collected during the study including your samples will still be used according to applicable laws

The Investigator must also contact the IRT to register the patient's discontinuation from study treatment.

### **9.1.2 Withdrawal of informed consent**

Subjects may voluntarily withdraw consent to participate in the study for any reason at any time. Withdrawal of consent occurs only when a subject:

- Does not want to participate in the study anymore, and
- Does not allow further collection of personal data

In this situation, the Investigator should make a reasonable effort (e.g. telephone, e-mail or letter) to understand the primary reason for the subject's decision to withdraw his/her consent and record this information.

Study treatment must be discontinued and no further assessments conducted, and the data that would have been collected at subsequent visits will be considered missing.

Further attempts to contact the subject are not allowed unless safety findings require communicating or follow-up.

All efforts should be made to complete the assessments prior to study withdrawal. A final evaluation at the time of the subject's study withdrawal should be made as detailed in the assessment table.

Novartis will continue to keep and use collected study information (including any data resulting from the analysis of a subject's samples until their time of withdrawal) according to applicable law.

For US: All biological samples not yet analyzed at the time of withdrawal may still be used for further testing/analysis in accordance with the terms of this protocol and of the informed consent form.

For EU and RoW: All biological samples not yet analyzed at the time of withdrawal will no longer be used, unless permitted by applicable law. They will be stored according to applicable legal requirements.

### **9.1.3 Lost to follow-up**

For subjects whose status is unclear because they fail to appear for study visits without stating an intention to discontinue or withdraw, the Investigator must show "due diligence" by documenting in the source documents steps taken to contact the subject, e.g. dates of telephone calls, registered letters, etc. A subject should not be considered as lost to follow-up until due diligence has been completed or until the end of the study.

### **9.1.4 Early study termination by the sponsor**

The study can be terminated by Novartis at any time for any reason. This may include reasons related to the benefit/ risk assessment of participating in the study, practical reasons (including slow enrollment), or for regulatory or medical reasons. In taking the decision to terminate, Novartis will always consider the patient welfare and safety. Should early termination be necessary, patients must be seen as soon as possible (provide instruction for contacting the

patient, when the patient should stop taking drug, when the patient should come for a final visit) and treated as a prematurely withdrawn patient. The Investigator may be informed of additional procedures to be followed in order to ensure that adequate consideration is given to the protection of the patient's interests. The Investigator or sponsor depending on the local regulation will be responsible for informing IRBs/IECs of the early termination of the trial.

## **9.2 Study completion and post-study treatment**

A patient will be considered to have completed the study when the patient has completed the last visit planned in the protocol. Study completion for a patient will occur after he/she has completed 16-weeks of treatment (through the follow-up visit) or they have prematurely withdrawn. Completion of the study will be when all randomized patients have completed 16 weeks of treatment and the post-treatment follow-up visit.

Patients who have been screened when enrolment target has been met will be allowed to proceed onto study participation.

For all patients a safety follow-up visit should be conducted (e.g. by telephone) 14 days after last visit (Week 16). The information to be collected at this follow up visit includes adverse events, concomitant medications and SAEs.

When the patient has completed all scheduled study assessments or prematurely withdrawn from the study, the Investigator must contact the IRT to record the patient completion /discontinuation and complete applicable eCRF .

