### 3 Study design

This is a Phase 3b, Proof-of-concept study with a randomized, multicenter, double-blind, placebo-controlled, parallel-group study design to determine the ability of fevipiprant plus SoC compared to placebo plus SoC to reduce the size of NPs. The study will include: Screening period of two weeks to assess eligibility; Run-in period of 4 weeks where patients will utilize mometasone furoate spray (200 µg once daily, administered as two 50 µg actuations into each nostril); Treatment period of 16 weeks (with visits held every month for study procedures); and a Follow-up period of two weeks following the last dose of study drug to collect additional data for safety variables. Patients will continue to use the mometasone furoate SoC throughout the Treatment period. Approximately 93 patients will be enrolled into this study. Please refer to [Table 8-1](#) for the clinical visit schedule and the details of procedures to be performed at each visit.

[figure not shown]

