**Table 8-1 Assessment Schedule**

Period	Screening			Treatment					
Visit Name	Screening	Run-in 		Treatment				EOT or TD	Follow-up
Days	-42 to -28	-28 to -1	1	1	28	56	84	112	124
Weeks	-6 to -4	-4 to -1	1	1	4	8	12	16	18
Informed consent	X								
Inclusion / Exclusion criteria	X	X	X						
Demography	X								
Physical Examination	S							S	
Medical history/current medical conditions	X								
Surgeries and Procedures	X								
Prior medications	X								
Safety Follow up Call									S
ACQ-5	X								
Vital Signs	X	X	X		X	X	X	X	
Body Height	X								
Electrocardiogram (ECG)	X		X					X	
Body Weight	X								
Pregnancy Test (serum)	X								
Pregnancy Test (Urine)			S		S	S	S	S	
Hematology	X		X			X		X	
HbA1C	X							X	
Clinical Chemistry	X		X			X		X	
Urinalysis	X		X						
Check IMP Compliance					S	S	S	S	
Contact IRT (IVRS/IWRS)	S	S	S	S	S	S	S	S	
Randomization				S					

Period	Screening			Treatment					
Visit Name	Screening	Run-in 		Treatment				EOT or TD	Follow-up
Days	-42 to -28	-28 to -1	1	1	28	56	84	112	124
Weeks	-6 to -4	-4 to -1	1	1	4	8	12	16	18
Study Drug Dispensation				S	S	S	S		
Study drug administration				Daily					
SoC/Rescue Medication Dispense		S	S	S	S	S	S		
Adverse Events	X	X	X		X	X	X	X	X
Serious Adverse Events	X	X	X		X	X	X	X	X
Concomitant medications	X	X	X		X	X	X	X	X
Liver Event Monitoring 	X	X	X	X	X	X	X	X	X
Renal Event Monitoring 	X	X	X	X	X	X	X	X	X
Nasal Endoscopy 	X		X			X		X	
Nasal Congestion Score Questionnaire	X	X	X		X	X	X	X	
QoL Questionnaire (SNOT-22)	X	X	X		X	X	X	X	
Smell Assessment (UPSIT)	X	X	X		X	X	X	X	
Study completion information								X	

X Assessment to be recorded in the clinical database or received electronically from a vendor

S Assessment to be recorded in the source documentation only

 Assessments at Run-in Day 1 will be performed prior to Randomization. Run-in Day 1 and the Treatment Day 1 visit will take place on the same day if the patient is randomized

 Please refer to protocol [Section 10.2.1](#)

 Please refer to protocol [Section 10.2.2](#)

 Nasal polyp score will be determined by central reading.

 [REDACTED]

 For patient familiarization with device only.

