All adverse events must be treated appropriately. Treatment may include one or more of the following:

- Dose not changed
- Dose Reduced/increased
- Drug interrupted/withdrawn

Conditions that were already present at the time of informed consent should be recorded in medical history of the subject.

Adverse events (including lab abnormalities that constitute AEs) should be described using a diagnosis whenever possible, rather than individual underlying signs and symptoms.

Adverse event monitoring should be continued for at least 14 days (or 5 half-lives or end of study visit, whichever is longer) following the last dose of study treatment

Information about adverse drug reactions for the investigational drug can be found in the Investigator Brochure (IB).

Abnormal laboratory values or test results constitute adverse events only if they fulfill at least one of the following criteria:

- they induce clinical signs or symptoms
- they are considered clinically significant
- they require therapy

Clinically significant abnormal laboratory values or test results must be identified through a review of values outside of normal ranges/clinically notable ranges, significant changes from

baseline or the previous visit, or values which are considered to be non-typical in subjects with the underlying disease. Alert ranges for laboratory and other test abnormalities are included in [Section 16.1](#).

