### **10.1.3 SAE reporting**

To ensure patient safety, every SAE, regardless of causality, occurring after the patient has provided informed consent and until 30 days following the last administration of study treatment must be reported to Novartis safety within 24 hours of learning of its occurrence. Detailed instructions regarding the submission process and requirements are to be found in the Investigator folder provided to each site.

All follow-up information for the SAE including information on complications, progression of the initial SAE and recurrent episodes must be reported as follow-up to the original episode within 24 hours of the Investigator receiving the follow-up information. An SAE occurring at a different time interval or otherwise considered completely unrelated to a previously reported one must be reported separately as a new event.

If the SAE is not previously documented in the Investigator's Brochure or Package Insert (new occurrence) and is thought to be related to the study treatment, a Chief Medical Office and Patient Safety Department associate may urgently require further information from the Investigator for health authority reporting. Novartis may need to issue an Investigator Notification (IN) to inform all Investigators involved in any study with the same study treatment that this SAE has been reported.

Suspected Unexpected Serious Adverse Reactions (SUSARs) will be collected and reported to the competent authorities and relevant ethics committees in accordance with EU Guidance 2011/C 172/01 or as per national regulatory requirements in participating countries.

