1.1 Study design

This study uses a randomized, multicenter, double-blind, placebo-controlled, parallel-group study design to determine the ability of fevipiprant plus SoC compared to placebo plus SoC to reduce the size of Nasal Polyps in patients with asthma.

The study will include a Screening period of 2 weeks to assess eligibility followed by run-in period of 4 weeks where the patients will utilize Mometasone Furoate spray (200µg once daily administered as two 50µg actuations into each nostril) for baseline assessments treatment. The patients would then enter a treatment period of 16 weeks (with visits held every months for study procedures) and a follow-up period of 2 weeks following the last dose of study drug to collect additional data for safety variables.

The study will follow a 1:1:1 central randomization in each of the three arms (450 µg Fevipiprant+SoC , 150 µg Fevipiprant+SoC and Placebo)

The primary analysis will be performed after all patients have completed 16 weeks of study treatment or have discontinued early.

Approximately 93 patients will be enrolled into this study.

No formal interim analyses would be performed.

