2.1.1 Data included in the analysis

The analysis cut off date is defined as the date of last patient last visit during the 2 week follow-up period post the 16 weeks treatment period. The entire data collected up to the cut off date would be used under the scope of the analysis defined in the subsequent sections. All data with an assessment date or even start date (e.g. vital sign assessment date or start date of an adverse event) prior to or on the cut off date will be included in the analysis. Any data collected beyond the cut-off date will not be included in the analysis and will not be used for any derivations.

All events with start date before or on the cut-off date and end date after the cut-off date will be reported as 'continuing at the cut-off date'. The same rule will be applied to events starting before or on the cut-off date and not having documented end date. This approach applies, in particular, to adverse event and concomitant medication reports. For these events, the end date will not be imputed and therefore will not appear in the listings

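### Table 8-1 prints the follow-up contact as Day 124 where its Week 18 label and the text imply Day 126; on either day completers have no scheduled contact for the last 16 to 18 days of the 30-day SAE window, and the SAP cut-off drops later data

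*Protocol*

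**What the plan says.** **Timing of the contact.** Protocol 9.2: "For all patients a safety follow-up visit should be conducted (e.g. by telephone) 14 days after last visit (Week 16". Protocol Section 3 describes a "Follow-up period of two weeks following the last dose of study drug to collect additional data for safety variables", and SAP 1.1 likewise has "a follow-up period of 2 weeks following the last dose of study drug to collect additional data for safety variables". The protocol summary agrees. In Table 8-1 the post-treatment contact is a "Safety Follow up Call" in the Follow-up column. That column is headed Week 18, but the Days row for the treatment and follow-up visits reads "28 56 84 112 124". No visit window is stated for the call.

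**Length of collection.** Protocol 10.1.1: "Adverse event monitoring should be continued for at least 14 days" after the last dose, or 5 half-lives or the end-of-study visit if either is longer. Protocol 10.1.3 requires every SAE occurring "until 30 days following the last administration of study treatment must be reported to Novartis safety within 24 hours" of the site learning of it. Protocol 12.5.1 uses the same 30 days to define on-treatment data and treatment-emergent events.

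**Cut-off.** SAP 2.1.1 sets the cut-off at the last patient's last visit in the 2-week follow-up and adds: "Any data collected beyond the cut-off date will not be included in the analysis". SAP 2.7.6 nevertheless plans a table of all deaths after the first dose.

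**The concern.** Three time spans should fit together: when the patient is last asked about events, how long events count, and when the data are cut. Here they do not.

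First, the printed day of the last contact falls before the end of the protocol's own minimum monitoring period. Second, the 30-day window, which is both a reporting duty and an analysis definition in the protocol, runs well past the last time anyone is scheduled to ask. Protocol 10.1.1 relies on non-directive questioning at each visit to find events, and a completer has no visit after this one. Third, the SAP closes the data before the 30 days have ended for patients who finish late.

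Safety and tolerability is a secondary objective. At stake is whether late serious events are sought equally over the period the protocol says it covers, and whether those that are reported reach the study report.

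**Working it through.** **Inputs**
- End-of-treatment visit: Day 112, Week 16 (Table 8-1).
- Last dose: Day 112. Protocol 6.6.1 has a dose taken at that visit from the returned medication.
- Follow-up contact: Day 124 (Days row); Week 18 (Weeks row); 14 days after Week 16 (9.2).
- Minimum AE monitoring: 14 days (10.1.1). Protocol 9.1.1 links 5 half-lives with at least one week, so I take 14 days as the binding figure.
- SAE reporting window: 30 days after the last dose (10.1.3).

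**Step 1: does the printed day agree with its week label?** The scheduled visits from Week 4 onward follow Day = 7 × Week: 7 × 4 = 28, 7 × 8 = 56, 7 × 12 = 84, 7 × 16 = 112. For Week 18, 7 × 18 = 126, and 112 + 14 = 126. The printed 124 is not reproduced. Counting from Day 1 does not rescue it either: 7 × 18 + 1 = 127.

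**Step 2: days covered after the last dose.** Gap = contact day − last-dose day. The window ends on Day 112 + 30 = 142.

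| Contact day | Gap from Day 112 | 14-day minimum | Share of 30 days | Days without scheduled contact |
|---|---|---|---|---|
| 124 | 12 | 2 days short | 12/30 = 40% | 142 − 124 = 18 (60%) |
| 126 | 14 | met exactly | 14/30 = 46.7% | 142 − 126 = 16 (53%) |

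If the last dose is a day earlier or later (Day 111 or 113), the gap is 13 or 11 days for a Day 124 contact, which never reaches 14. For a Day 126 contact it is 15 or 13 days.

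**Step 3: who is affected.** Patients who stop treatment early should, where possible, keep to the visit schedule or be telephoned on it (9.1.1). If they do so through to Day 126, anyone whose last dose is on or before Day 126 − 30 = 96 is contacted at least 30 days after it. The gap therefore concerns completers and those who stop after about Day 96. As an illustration, if the 10% dropout in Protocol 12.8.1 is taken as the share not completing treatment, 93 × 0.90 = 83.7, or about 84 patients.

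**Step 4: reach of the cut-off.** With the last patient's contact at Day 126, the cut-off precedes the end of that patient's 30 days by 142 − 126 = 16 days. A patient whose contact fell k days before the cut-off loses 16 − k days, so only those with contacts in the final 16 days of the study are touched. SAP 2.1.3.9 already keeps post-treatment data other than deaths out of the safety summaries (on-treatment ends at last dose + 1 day). For these late events, the cut-off therefore changes the listings and the all-deaths table. SAP 2.7.4 also mentions selected tables on all data after first intake, but it does not name them and I do not count them.

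**The case against.** The strongest reply is that Day 124 is a slip in one cell. The Week 18 label, 9.2, Section 3, the summary and SAP 1.1 all give two weeks, and on that timing the 14-day minimum is met. This stands in part. A reader might infer that the trial is designed to contact patients at 12 days and so to miss its own minimum; the documents do not support that, because most of them say 14. But Table 8-1 is the schedule that sites work from, and no window absorbs the 2 days.

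The second reply is that 10.1.3 is a duty to report what the site learns, not a promise of a contact at 30 days. That also stands. A reader might infer that SAE collection stops at the call; it does not. Events can be volunteered between visits (10.1.1), and a volunteered SAE must still be reported. A call at 14 days also falls after the one week that 9.1.1 links with 5 half-lives. What remains is that active questioning ends before half of the window has passed, although 12.5.1 uses the whole window as an analysis period.

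The third reply is that the cut-off matters little. A reader might infer that it removes late SAEs from the main safety tables. It does not, because the SAP's 1-day rule has already left them out. That rule conflicts with the 30 days in Protocol 12.5.1, but this is a separate point. The report to sponsor safety is unaffected. The loss from the listings and the all-deaths table remains.

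**Conclusion.** The point holds in three limited parts.

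- Table 8-1 contradicts itself and the text by 2 days (Day 124 against Day 126). The shortfall against the 14-day minimum arises only if a site follows the Days row.
- On either day, patients who complete treatment have no scheduled contact for 16 days (Day 126) or 18 days (Day 124) of the 30-day window.
- The SAP cut-off excludes up to 16 days of reportable SAEs and deaths for the last patients, with the contact at Day 126. This conflicts with the planned table of all deaths after first dose.

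It would be wrong to extend this to all 93 patients, since early discontinuers can have later contacts. The figures assume a last dose on Day 112. The number of events that might be missed cannot be estimated: Protocol 4.5 counts SAEs in earlier studies but gives no denominator or time at risk for them. The point is worth correcting because the remedy is specific and cheap, not because a large loss has been shown.

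**What to change.** 1. Reconcile the Days row of Table 8-1 with its Week 18 label, Protocol 9.2 and Protocol 10.1.1, so that one day is stated throughout.
2. Reconcile the timing of the final safety contact with the 30-day window in Protocol 10.1.3 and 12.5.1. The existing call could be made later, or a brief call about SAEs and deaths could be added.
3. In SAP 2.1.1, define the cut-off for SAEs and deaths as the end of the last patient's 30-day window, so that it agrees with SAP 2.7.6.

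The cost is more than a table correction. The two-week follow-up also appears in the protocol summary, Section 3, 9.2 and SAP 1.1, so a change in the contact needs a protocol amendment under Protocol 14.1. Operationally it is the same telephone call made later, or one short extra call, and a database lock about 142 − 126 = 16 days later.
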